10.4 Schedule of Visits, Measurements and Dosing

10.4.1 Scheduled Visits

Refer to [Appendix 1](#) for a schedule of visits and measurements.

10.4.2 Unscheduled Visits

These visits may be performed in order to ensure subject safety. All procedures performed at an unscheduled visit will be recorded in the source documents and on the Unscheduled Visit eCRF pages. Any procedure indicated in the eCRF that is not performed should be indicated as “Not done.”

Evaluations that may be conducted at an Unscheduled Visit include:

- Vital Signs
- Labs
- Slit-lamp Biomicroscopy
- Visual Acuity
- Intraocular Pressure
- Urine Pregnancy Test
- Ophthalmoscopy
- Assessment of Adverse Events
- Assessment of concomitant medications and/or treatments
- Any other assessments needed in the judgment of the investigator.

10.5 Compliance with Protocol

Whilst subjects are dosed at site, they will receive their study treatment directly from the investigator or designee, under medical supervision. The date and time of each dose administered in the clinic will be recorded in the source documents. The dose of study treatment and study subject identification will be confirmed at the time of dosing by a member of the study site staff other than the person administering the study treatment.

Subjects will be instructed on proper instillation and storage of study drug at the end of Visits 1, 2, 3, and 4, and given written instructions. The used and unused study drug vials will be collected at each visit from Visit 2 up to and including Visit 5 to assess dosing and symptom assessment compliance. Dosing compliance will be based off of the used and unused vial count. If the subject is less than 80% or more than 125% compliant with dosing based on the expected number of used vials, then the subject will be deemed non-compliant and a deviation should be recorded.

10.6 Subject Disposition

10.6.1 Completed Subjects

A completed subject is one who has not been discontinued from the study.

10.6.2 Discontinued Subjects

Subjects may be discontinued prior to their completion of the study due to:

- subject request/withdrawal
- AEs
- protocol violations
- administrative reasons (e.g., inability to continue, lost to follow up)
- sponsor termination of study
- other

Note: In addition, any subject may be discontinued for any sound medical reason.

Notification of a subject discontinuation and the reason for discontinuation will be made to Ora and/or sponsor and will be clearly documented on the CRF.

10.7 Study Termination

The study may be stopped at any time by the investigator, the sponsor, and/or Ora with appropriate notification.

10.8 Study Duration

The total duration of study is approximately 3.5 months (from screening to study completion).

10.9 Monitoring and Quality Assurance

During the course of the study a monitor, or designee, will make routine site visits to review protocol compliance, assess Investigational Product (IP)/device accountability, and ensure the study is being conducted according to the pertinent regulatory requirements. The review of the subjects' medical records will be performed in a manner that adequately maintains subject confidentiality. Further details of the study monitoring will be outlined in a monitoring plan.

Regulatory authorities of domestic and foreign agencies, Ora, Inc. quality assurance and or its designees may carry out on-site inspections and/or audits which may include source data checks. Therefore, direct access to the original source data will be required for inspections and/or audits. All inspections and audits will be carried out giving consideration to data protection as well as subject confidentiality to the extent that local, state, and federal laws apply.

11 ADVERSE EVENTS

11.1 Adverse Event

An AE is defined as any untoward medical occurrence associated with the use of an IP in humans, whether or not considered IP-related. An AE can be any unfavorable and unintended sign (e.g., an abnormal laboratory finding), symptom, or disease temporally associated with the use of an IP, without any judgment about causality. An AE can arise from any use of the IP (e.g., off-label use, use in combination with another drug or medical device) and from any route of administration, formulation, or dose, including an overdose. An AE can arise from any delivery, implantation, or use of a medical device, including medical device failure, subject characteristics that may impact medical device performance (e.g., anatomical limitations), and therapeutic parameters (e.g., energy applied, sizing, dose release, and anatomic fit) associated with medical device use.

All AEs spontaneously reported by the subject and/or in response to an open question from study personnel or revealed by observation, physical examination or other diagnostic procedures will be recorded in the source document and on the appropriate pages of the CRF. Any clinically relevant deterioration in clinical finding is considered an AE and must be recorded. When possible, signs and symptoms indicating a common underlying pathology should be noted as one comprehensive event.

Documentation regarding the AE should be made as to the nature, date of onset, end date, severity, and relationship to IP, action(s) taken, seriousness, and outcome of any sign or symptom observed by the physician or reported by the subject upon indirect questioning.

11.1.1 Severity

Severity of an AE is defined as a qualitative assessment of the degree of intensity of an AE as determined by the investigator or reported to him/her by the subject. The assessment of severity is made irrespective of relationship to IP or seriousness of the event and should be evaluated according to the following scale:

- ***Mild:*** Event is noticeable to the subject, but is easily tolerated and does not interfere with the subject's daily activities.
- ***Moderate:*** Event is bothersome, possibly requiring additional therapy, and may interfere with the subject's daily activities.
- ***Severe:*** Event is intolerable, necessitates additional therapy or alteration of therapy, and interferes with the subject's daily activities.

11.1.2 Relationship to Investigational Product

A determination will be made of the relationship (if any) between an adverse event and the study drug or study procedure, as applicable. A causal relationship is present if a determination is made that there is a reasonable possibility that the adverse event may have been caused by the drug or study procedure.

The relationship of each AE to the IP should be determined by the investigator using these explanations:

- **Suspected:** A reasonable possibility exists that the IP caused the AE. A suspected AE can be further defined as:
 - *Definite:* Relationship exists when the AE follows a reasonable sequence from the time of IP administration, follows a known response pattern of the drug class, is confirmed by improvement on stopping the IP and no other reasonable cause exists.
 - *Probable:* Relationship exists when the AE follows a reasonable sequence from the time of IP administration, follows a known response pattern of the drug class, is confirmed by improvement on stopping the IP and the suspect IP is the most likely of all causes.
 - *Possible:* Relationship exists when the AE follows a reasonable sequence from the time of IP administration, but could also have been produced by the subject's clinical state or by other drugs administered to the subject.
- **Not Suspected:** A reasonable possibility does not exist that the IP caused the AE.
 - *Not Related:* Concurrent illness, concurrent medication, or other known cause is clearly responsible for the AE, the administration of the IP and the occurrence of the AE are not reasonably related in time, OR exposure to IP has not occurred.

Suspected adverse reaction means any AE for which there is a reasonable possibility that the IP caused the AE. “Reasonable possibility” means there is evidence to suggest a causal relationship between the IP and the AE. Types of evidence that would suggest a causal relationship between the IP and the AE event include: a single occurrence of an event that is uncommon and known to be strongly associated with IP exposure (e.g., angioedema, hepatic injury, Stevens-Johnson Syndrome); one or more occurrences of an event that is not commonly associated with IP exposure, but is otherwise uncommon in the population exposed to the IP (e.g., tendon rupture); an aggregate analysis of specific events observed in a clinical trial (such as known consequences of the underlying disease or condition under investigation or other events that commonly occur in the study population independent of drug therapy) that indicates those events occur more frequently in the IP-treatment group than in a concurrent or historical control group.

11.1.3 Expectedness

The expectedness of an AE should be determined based upon existing safety information about the IP using these explanations:

- **Unexpected:** An AE that is not listed in the Investigator's Brochure (IB) or is not listed at the specificity or severity that has been observed.
- **Expected:** An AE that is listed in the IB at the specificity and severity that has been observed.
- **Not applicable:** An AE unrelated to the IP.

AE events that are mentioned in the IB as occurring with a class of products or as anticipated from the pharmacological/mechanical (or other) properties of the product, but are not specifically mentioned as occurring with the particular product under investigation are to be considered unexpected.

The investigator should initially classify the expectedness of an AE, but the final classification is subject to the Medical Monitor's determination.

11.2 Serious Adverse Events

An AE is considered serious if, in the view of either the investigator or sponsor, it results in any of the following outcomes:

- Death;
- A life-threatening AE;

Note: An AE is considered "life-threatening" if, in the view of either the investigator or sponsor, its occurrence places the subject at immediate risk of death. It does not include an AE that, had it occurred in a more severe form, might have caused death.

- Inpatient hospitalization or prolongation of existing hospitalization;

Note: The term "inpatient hospitalization" refers to any inpatient admission (even if less than 24 hours). For chronic or long-term inpatients, inpatient admission includes transfer within the hospital to an acute/intensive care inpatient unit. Inpatient hospitalization does not include: emergency room visits; outpatient/same-day/ambulatory procedures; observation/short stay units; rehabilitation facilities; hospice facilities; nursing homes; or clinical research/phase 1 units.

Note: The term "prolongation of existing hospitalization" refers to any extension of an inpatient hospitalization beyond the stay anticipated or required for the reason for the initial admission as determined by the investigator or treating physician.

- A persistent or significant incapacity or substantial disruption of the ability to conduct normal life functions;

Note: A serious adverse event (SAE) specifically related to visual threat would be interpreted as any potential impairment or damage to the subject's eyes (e.g., hemorrhage, retinal detachment, central corneal ulcer or damage to the optic nerve).

- A congenital anomaly/birth defect.

Important medical events that may not result in death, are life-threatening, or require hospitalization may be considered serious when, based upon appropriate medical judgment, they may jeopardize the subject and may require medical or surgical intervention to prevent one of the outcomes listed in this definition.

11.3 Procedures for Reporting Adverse Events

All AEs and their outcomes must be reported to Ora, the sponsor, and the IRB/IEC as required by the IRB/IEC, federal, state, or local regulations and governing health authorities and recorded on the appropriate CRF.

11.3.1 Reporting a Suspected Unexpected Adverse Reaction

All AEs that are ‘suspected’ and ‘unexpected’ are to be reported to Ora, the sponsor and the IRB/IEC as required by the IRB/IEC, federal, state, or local regulations and governing health authorities.

11.4 Procedures for Unmasking (if applicable)

When necessary for the safety and proper treatment of the patient, the investigator can unmask the patient’s treatment assignment to determine which treatment has been assigned and institute appropriate follow-up care. When possible, the sponsor

(AxeroVision Inc.) should be notified prior to unmasking study medication. The investigator should inform the sponsor (AxeroVision Inc.) of the unmasking if there is no notification prior to the unmasking.

A report of the results of this study may be published, sent to the appropriate health authorities in any country in which the study drug may ultimately be marketed, and published in part as required by appropriate health authorities (e.g., Clinical Trials posting and disclosure), but the patient's name will not be disclosed in these documents.

Patients will be informed that the study is posted and the results eventually disclosed by appropriate health authorities (e.g., Clinical Trials posting or freedom of information by the FDA).

11.5 Type and Duration of the Follow-up of Subjects after Adverse Events

Any serious adverse event occurring during the study period (beginning with informed consent) and for at least 12 weeks after the last dose of study drug must be immediately reported, but no later than 24 hours after learning of a serious adverse event. Serious adverse events must be reported to AxeroVision Inc. (or Agent of AxeroVision Inc.) as listed on the AxeroVision Inc. Study Contacts Sheet and recorded on the serious adverse event form. All patients with a serious adverse event must be followed up and the outcomes reported. The investigator must supply AxeroVision Inc. and the IRB/IEC with any additional requested information (e.g., autopsy reports and discharge summaries).

In the event of a serious adverse event, the investigator must:

1. Notify AxeroVision Inc. immediately by fax or email using the serious adverse event form (contact details can be found on page 1 of the serious adverse event form); phone numbers and relevant AxeroVision Inc. personnel contacts are also on the front page of the protocol.
2. Obtain and maintain in his/her files all pertinent medical records, information, and medical judgments from colleagues who assisted in the treatment and follow-up of the patient.
3. Provide AxeroVision Inc. with a complete, written description of the adverse event(s) on the serious adverse event form describing the event chronologically, including any treatment given (e.g., medications administered, procedures performed) for the adverse event(s). Summarize relevant clinical information about the event: signs, symptoms, diagnosis, clinical course and relevant clinical laboratory tests, etc. Include any additional or alternative explanation(s) for the causality which includes a statement as to whether the event was or was not related to the use of the investigational drug.

4. Promptly inform the governing IRB/IEC of the serious adverse event as required by the IRB/IEC, local regulations, and the governing health authorities.

12 STATISTICAL HYPOTHESES AND METHODS OF ANALYSES

The statistical analysis plan (SAP) will provide a detailed description of the planned statistical analysis.

12.1 Sample Size Determination

The sample size is determined empirically. Xiidra achieved a 0.25 unit difference between lifitegrast ophthalmic solution and vehicle in mean change from baseline to day 84 in inferior cornel staining and a standard deviation of approximately 0.75 in Phase 2. Sample sizes for this study are based on detecting a 0.35 unit difference between the active and vehicle groups, assuming a standard deviation of 0.75. In Stage 1 the number of expected enrolled subjects varies between 43 and 53 subjects in the active group and between 37 and 47 subjects in the vehicle group. In Stage 2 the number of expected enrolled subjects is 60 in the active group and 30 to 60 subjects in the vehicle group. Thus, the combined sample provides between 103 and 113 subjects in the active group and between 67 and 77 subjects in the matching vehicle group or between 97 and 107 subjects in the combined vehicle group. Under these assumptions and allowing a dropout rate of 10%, sample sizes of 93 in the active treatment group and 60 in the vehicle group will yield 80% power to show a significant difference at the $\alpha = 0.05$ level using a two-sample t-test.

12.2 Analysis Populations

The following analysis populations will be considered:

- Modified Intent-to-Treat Population – The modified intent-to-treat (mITT) population includes all randomized subjects that have baseline and at least 1 post-baseline assessment for 1 or more of the efficacy measurements (see [Section 8.1](#)). The primary analysis will be performed on the mITT population with the Last Observation Carried Forward (LOCF) imputation method for missing values. The mITT population may also be analyzed with observed data only (i.e., without LOCF) and using multiple imputation methods to assess sensitivity. Subjects in the mITT population will be analyzed as randomized.
- Modified Intent-to-Treat 2 Population – The modified intent-to-treat 2 (mITT2) population includes all subjects in the mITT population that have baseline inferior corneal staining score in the study eye > 1.5 . The mITT2 population will be analyzed using LOCF. The mITT2 population may also be analyzed using observed data only to assess sensitivity. Subjects in the mITT2 population will be analyzed as randomized.
- Per Protocol Population – The per protocol (PP) population includes subjects in the mITT population who do not have significant protocol deviations and who

complete the study. Protocol deviations will be assessed prior to database lock and unmasking. The PP population will be analyzed using observed data only for primary efficacy variables. Subjects in the PP population will be analyzed as treated.

- **Safety Population** – The safety population includes all randomized subjects who have received at least one dose of the investigational product. The safety population will be analyzed for all safety assessments. Subjects in the Safety population will be analyzed as treated.

The statistical analysis of safety data will be performed for the safety population. The analysis of baseline and efficacy data will be performed for the mITT population. The primary efficacy analysis will also be performed on the mITT2 and PP populations as sensitivity analyses.

12.3 Statistical Hypotheses

The statistical hypotheses are stated in terms of one-sided hypotheses, although statistical testing will be two-sided. All hypotheses are Pre-CAE®.

H_{01} : There is no difference between AXR-159 Ophthalmic Solution (50 mg/ml, 30 mg/ml or 3 mg/ml, TID or BID) and vehicle (TID or BID) in the change from baseline to Month 3 in inferior corneal staining score in the study eye.

H_{11} : The change from baseline to Month 3 in inferior corneal staining score in the study eye is less with AXR-159 Ophthalmic Solution (50 mg/ml, 30 mg/ml or 3 mg/ml, TID or BID) than with vehicle (TID or BID).

H_{02} : There is no difference between AXR-159 Ophthalmic Solution (50 mg/ml, 30 mg/ml or 3 mg/ml, TID or BID) and vehicle (TID or BID) in the change from baseline to Month 3 in total corneal staining score in the study eye.

H_{12} : The change from baseline to Month 3 in total corneal staining score in the study eye is less with AXR-159 Ophthalmic Solution (50 mg/ml, 30 mg/ml or 3 mg/ml, TID or BID) than with vehicle (TID or BID).

H_{03} : There is no difference between AXR-159 Ophthalmic Solution (50 mg/ml, 30 mg/ml or 3 mg/ml, TID or BID) and vehicle (TID or BID) in the change from baseline to Month 3 in eye dryness.

H_{13} : The change from baseline to Month 3 in eye dryness is less with AXR-159 Ophthalmic Solution (50 mg/ml, 30 mg/ml or 3 mg/ml, TID or BID) than with vehicle (TID or BID).

H_{04} : There is no difference between AXR-159 Ophthalmic Solution (50 mg/ml, 30 mg/ml or 3 mg/ml, TID or BID) and vehicle (TID or BID) in the change from baseline to Month 3 in total OSDI score.

H14: The change from baseline to Month 3 in total OSDI score is less with AXR-159 Ophthalmic Solution (50 mg/ml, 30 mg/ml or 3 mg/ml, TID or BID) than with vehicle (TID or BID).

In the hypotheses above, dosing (TID or BID) of the vehicle will match the dosing of the active treatment.

12.4 Statistical Analyses

12.4.1 General Approach

In general, continuous data will be summarized with descriptive statistics (number of subjects, mean, standard deviation, median, minimum, and maximum) and will be analyzed using analysis of variance (ANOVA), analysis of covariance (ANCOVA) techniques, two-sample t-tests or Wilcoxon rank sum tests for between-group comparisons, and paired t-tests or sign-rank tests for within-group analyses. Categorical variables will be summarized by number of subjects (n), frequency counts, and percentages, and they will be analyzed using Pearson's chi-square test or Fisher's exact test (if the expected cell count is less than 5 in 25% or more of the cells). Ordinal variables will be analyzed using the Cochran-Mantel-Haenszel (CMH) or the Wilcoxon rank-sum test for between-treatment comparisons and the sign-rank test for within-treatment comparisons.

All summaries will be presented by treatment group and visit. Summaries will be provided for demographics, baseline medical history, concurrent therapies, and subject disposition.

For the purpose of summarization, medical history, concurrent therapies, and adverse events will be coded to MedDRA and WHO Drug dictionaries, as appropriate.

Baseline measures are defined as the last measure prior to the initiation of study treatment, usually at Day 1. If a measure is taken both pre-CAE® and post-CAE®, the baseline will be the last time point matched value prior to the initiation of study treatment. For post-CAE® measures, this will be at Day -14. For changes from pre-CAE® to post-CAE® post first treatment, the change from pre-CAE® to post-CAE® at Day -14 will be considered the baseline value.

Changes from baseline will be calculated as visit – baseline and summarized by treatment and visit as described above. Treatment comparisons between an active treatment and vehicle will be calculated as active – vehicle.

All primary and secondary analyses will be two-sided at a significance level of 0.05. 95% confidence intervals will be provided where appropriate.

12.4.2 Unit of Analysis

Safety endpoints will be analyzed for both eyes. For efficacy endpoints, the unit of analysis will be the study eye, or the “worst eye,” as defined by the following:

Study Eye/Worst Eye: Eyes are eligible for analysis if they meet all of the inclusion criteria. In the case that both eyes are eligible for analysis, the study eye will be the eye with worse (higher) inferior corneal staining score (Ora Calibra® scale) on Day 1. If the inferior corneal staining score is the same in both eyes, then the right eye will be selected as the study eye.

12.4.3 Missing Data

The primary efficacy analyses will be performed using Last Observation Carried Forward (LOCF) methodology. For the LOCF analyses of the primary efficacy variables at Month 3, the last value from the previous visits will be carried forward, matching pre-CAE® or post-CAE® time points. A pre-CAE® time point will never be imputed for a post-CAE® value, and vice versa.

An analysis using observed data only will also be performed for the primary efficacy variables. As additional sensitivity analyses, Markov Chain Monte Carlo (MCMC) multiple imputation methodology may be used to impute missing data for the analyses of the primary efficacy variables.

No secondary efficacy endpoints or safety endpoints will be imputed.

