10.2.2 Rescue Medications

In the event that rescue medication is required for worsening signs or symptoms of dry eye disease during the course of the study, patients will be provided an appropriate rescue regimen by the investigator/treating clinician, and will be exited from the study.

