10.3.1.3 Visit 3: 2-Week Follow-up (Day 15 ± 2 Days)

- Study drug collection
- Medical/medication history update
- Patient symptoms using the visual analog scale
- Ocular Discomfort Score
- OSDI
- SANDE

- BCVA with manifest refraction
- Bulbar conjunctival hyperemia scores (Ora Calibra® Conjunctival Redness for Dry Eye Scale)
- Slit-lamp biomicroscopy
- Oculus Keratograph 5® procedures: TBUT and tear meniscus height (selected sites)
- TFBUT
- Sodium fluorescein corneal staining, using the Oxford scale and Ora Calibra® scales
- Lissamine green conjunctival staining, using the Oxford scale
- 15+ minute wait from end of Lissamine staining to start of Schirmer's Test
- Schirmer without anesthesia
- Intraocular pressure (IOP)
- Dispense study drug
- Administer AXR-159 Ophthalmic Solution or vehicle in both eyes)
- Adverse event query

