10.3.1.4 Visit 4: Month 1.5 Follow-up (Day 43 ± 2 Days)

- Study drug collection
- Medical/medication history update
- Patient symptoms using the visual analog scale
- Ocular Discomfort Score
- OSDI
- SANDE
- BCVA with manifest refraction

- Bulbar conjunctival hyperemia scores (Ora Calibra® Conjunctival Redness for Dry Eye Scale)
- Slit-lamp biomicroscopy
- Oculus Keratograph 5® procedures: TBUT and tear meniscus height (selected sites)
- TFBUT
- Sodium fluorescein corneal staining, using the Oxford scale and Ora Calibra® scales
- Lissamine green conjunctival staining, using the Oxford scale
- 15+ minute wait from end of Lissamine staining to start of Schirmer's Test
- Schirmer without anesthesia
- Intraocular pressure (IOP)
- Dispense study drug
- Blood sample collection for systemic pharmacokinetics (in selected Stage 1 patients)
 - Collected pre-dose, and at 15, 30, 60, 90, 180, 360 minutes post-dose
- Administer AXR-159 Ophthalmic Solution or vehicle in both eyes (must NOT be done before blood and tear sample collection)
- Ora Calibra® Drop Comfort Assessment
- Adverse event query

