12.4.5 Primary Efficacy Analyses

The primary efficacy variables (Pre-CAE®) are:

- Change from Baseline to Month 3 in inferior corneal staining score (Ora Calibra® scale) in the study eye
- Change from Baseline to Month 3 in total corneal staining score (Oxford and Ora Calibra® scales) in the study eye
- Change from Baseline to Month 3 in eye dryness measured using a visual analogue scale (VAS)
- Change from Baseline to Month 3 in Total Ocular Surface Disease Index (OSDI) score, and

The primary variables will be summarized as described in [Section 12.4.1](#). The primary efficacy analysis will use the mITT population with LOCF.

Statistical tests will be performed for each AXR-159 Ophthalmic Solution group versus vehicle group at matched dosing frequency (TID or BID). ANCOVA models will be used to compare the change from baseline primary efficacy variables. The ANCOVA models will include terms for baseline value, baseline inferior corneal staining score (ICCS) and baseline eye dryness score as covariates and treatment (AXR-159 or vehicle) as a factor in the model. Pairwise comparisons will be performed for each AXR-159 treatment group versus vehicle using t-tests of the least square means from this model. Two-sided confidence intervals (95%) will be provided for the differences between treatments. As supportive analyses, two-sample t-tests and Wilcoxon rank sum tests will also be conducted.

Details of additional supportive primary efficacy analyses will be provided in the statistical analysis plan.

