8.2 Missing or Inconclusive Data Handling

The primary efficacy analyses will be performed using LOCF methodology. For the LOCF analyses of the pre-CAE® primary efficacy variables at Month 3 (Visit 5 [Day 85 ± 2]), the last value from the previous visits will be carried forward. Only pre-CAE® or non-CAE® time points will be used to impute a missing pre-CAE® value.

An analysis using observed data only will also be performed for the primary efficacy variables. As additional sensitivity analyses, Markov Chain Monte Carlo (MCMC) multiple imputation methodology will be used to impute missing data for the analyses of the primary efficacy variables.

No secondary efficacy endpoints or safety endpoints will be imputed.

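### LOCF lets Day 15 or Day 43 scores stand in for Month 3 in the primary analysis; an all-visit repeated-measures model would be a cheap improvement

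*Protocol*

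**What the plan says.** The primary variables are changes to Month 3, for example "Change from Baseline to Month 3 in inferior corneal staining score (Ora Calibra® scale) in the study eye" (Protocol 12.4.5). Both documents analyse them on the mITT population with LOCF: "The primary efficacy analyses will be performed using Last Observation Carried Forward (LOCF) methodology" (Protocol 12.4.3) and "The primary efficacy analyses will be performed using LOCF methodology" (SAP 8.2).

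The two documents describe the carried value differently. In the protocol, "the last value from the previous visits will be carried forward, matching pre-CAE® or post-CAE® time points". In the SAP, "Only pre-CAE® or non-CAE® time points will be used to impute a missing pre-CAE® value". Visits 3 (Day 15) and 4 (Day 43) are labelled non-CAE in the visit schedules, so it is the SAP sentence that clearly admits them. SAP section 1 says that its methods supersede the protocol's.

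The primary model (SAP 13.1.1) is an ANCOVA with one value per patient. Planned sensitivity analyses are observed data only, MCMC multiple imputation, and LOCF on the mITT2 and PP populations. The imputation code runs by treatment and names only the baseline and Visit 5 scores.

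Protocol 10.2.2 covers outcome-related exits: "In the event that rescue medication is required for worsening signs or symptoms of dry eye disease during the course of the study", the patient receives a rescue regimen and leaves the study. Neither document justifies LOCF.

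**The concern.** The question is the drug effect at Month 3. A patient who leaves after Day 15 answers a different one, the effect at two weeks, and LOCF records that answer as Month 3. This is harmless only if mean scores are flat from the carried visit onward, and the documents do not argue that they are.

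Efficacy at the end of Stage 1 informs which groups the DRC continues or judges futile (Protocol 6.1), and the final analysis declares significance at two-sided p < 0.05 (Protocol 12.4.8). A shrunken estimate could count against a useful group, and a false difference could favour an ineffective one. Staining, eye dryness and OSDI are scheduled at Days 15 and 43 for every patient, yet no planned model of the primary endpoints uses those visits longitudinally.

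**Working it through.** **Inputs from the documents** (Protocol 12.1, SAP 5): difference 0.35, SD 0.75, two-sided alpha 0.05, 10% dropout overall with no arm split, and combined enrolment of at least 103 active and 67 matching vehicle.

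**The plan's own figure.** 103 × 0.9 = 92.7 and 67 × 0.9 = 60.3, so 93/60 are the patients left after dropout. A two-sample t-test on 93/60 has 79.96% power (noncentral t), which reproduces the stated 80%. With all 103/67 observed, power is 84.0%.

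**Bias formula.** Let dA and dV be the exit shares, mA and mV the true mean Month 3 changes, and f the share of that change reached at the carried visit (same f in both arms). For exits unrelated to outcome:

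bias = (1 − f) × (−dA·mA + dV·mV)

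At f = 1 the bias is zero. At f = 0 the carried value equals baseline. That limit is possible: Day 1 is itself a non-CAE visit, and a patient can enter mITT through a different measure. Values of f, mA, mV and the arm split are assumptions.

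Power uses SE = 0.75 × √(1/103 + 1/67) = 0.118.

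**Equal exits, 10%/10%, true difference −0.35.** Bias = 0.10 × (1 − f) × 0.35.

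| f | bias | estimate | power |
|---|---|---|---|
| 0 | +0.035 | −0.315 | 76% |
| 0.5 | +0.0175 | −0.33 | 80% |
| 0.75 | +0.009 | −0.34 | 82% |

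Bias is therefore present without any difference in exits.

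**Exits 15% active, 5% vehicle**, with mA = −0.55 and mV = −0.20:
- f = 0.5: 0.5 × (0.0825 − 0.010) = +0.036, estimate −0.31, power 75%.
- f = 0.25: 0.75 × 0.0725 = +0.054, estimate −0.30, power 70%.

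**Exits 5% active, 17.7% vehicle.** At f = 0:
- mA = −0.70, mV = −0.35: 0.035 − 0.062 = −0.027 (effect enlarged).
- mA = −0.35, mV = 0: 0.0175 − 0 = +0.0175 (effect shrunk).

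The sign depends on the time course as well as on which arm loses more patients.

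**No drug effect, both arms improving by 0.6.**
- Equal exits: bias 0, type I error 5%.
- 15% vs 5%, f = 0.5: 0.10 × 0.5 × 0.6 = 0.030, type I error 5.7%.
- 21% vs 5%, f = 0.5: 0.16 × 0.5 × 0.6 = 0.048, type I error 6.9%.

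Values of f nearer 0 push this higher: with 0.5 improvement, exits of 20% vs 5% and f = 0, it is 9.7%.

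**Simulation** (103/67, correlation 0.6, effect growing over visits) agrees:
- 10%/10%: LOCF about −0.33 and 79% power; likelihood-based model about 80%.
- 15% active (mostly early) vs 5% vehicle: LOCF about −0.30 to −0.32 and 70-78%; likelihood-based 82-83%.
- No effect, both arms improving 0.6: type I error about 5% at equal exits, and 6-8% at 15-21% vs 2-5%.

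**Outcome-related exits.** With the worst patients leaving, a true −0.35, visit correlations of 0.5-0.6 and several exit splits, mean LOCF estimates ran from −0.27 to −0.35 and observed-data estimates from −0.14 to −0.50. Making the observed-data analysis primary would be no cure.

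**The case against.** The strongest reply is that the effect is small at the planned dropout, efficacy is labelled exploratory (SAP 8.5), and alternatives to LOCF are already planned. Much of this stands. At balanced 10% exits the loss is about one point of power. The SAP commits to an MCMC analysis that the protocol left optional, and the same measures are analysed visit by visit on observed data (SAP 13.2), so a marked divergence from LOCF should show. These analyses do not close the gap. With only baseline and Visit 5 in the imputation model, they cannot condition on the Day 15 and Day 43 scores that may precede an exit.

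A reader might infer several stronger things that the documents do not support:

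- That the design makes unequal exits likely. Only a 10% overall rate is given, a Stage 1 regimen is expanded only if judged safe and well tolerated, and the rescue rule applies to every arm.
- That bias needs unequal exits. The equal-exit case shows otherwise.
- That vehicle exits for lack of effect always inflate the result. One simulated case (19% vehicle, 7% active) gave −0.38, but the outcome-related runs above gave almost no inflation.
- That the type I error is seriously inflated. It stays near 5% unless exits are very uneven and the carried scores fall well short of the Month 3 change.
- That the protocol sentence alone brings in Days 15 and 43. Read literally, its matching rule could leave only the screening visit as an earlier pre-CAE value; the SAP settles it.

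The calculations use t-tests. The planned analysis and the proposed model both adjust for baseline covariates, so the figures are indicative.

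**Conclusion.** The point holds as a cheap improvement; it does not invalidate the plan. Under the SAP, Day 15 or Day 43 scores replace missing Month 3 scores, and the estimate is biased whenever scores or the drug effect are still changing after those visits. Size and direction depend on the time course and on who exits, and rescue makes some exits outcome-related. At 10% balanced exits the cost is about 0.02 units and one point of power. At 15% active (mostly early) vs 5% vehicle it is about 0.03 to 0.05 units and roughly 4 to 13 points. Everything beyond the sample sizes, the 0.35 difference, the SD of 0.75 and the 10% dropout is assumed.

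**What to change.** Amend the SAP before unmasking:

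1. Make the primary analysis a mixed model for repeated measures on change at Days 15, 43 and 85. Include treatment, visit, treatment by visit, baseline value of the endpoint, baseline inferior corneal staining and baseline eye dryness (a baseline that duplicates the endpoint's own enters once), with unstructured covariance. Report the Day 85 contrast against vehicle at matched dosing frequency.
2. Keep the LOCF ANCOVA and the observed-data ANCOVA as sensitivity analyses.
3. Add the Visit 3 and Visit 4 scores to the VAR statement of the MCMC imputation.
4. Add one reference-based or delta-adjusted run. The repeated-measures model assumes that exits depend on observed data, and worsening between visits that leads to rescue may not meet that assumption.
5. Record the change in SAP section 18, which currently reports no departures from the protocol.

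The cost is a SAP revision and some programming, with no new visits or patients. The stated sample size can stay: unadjusted power is 80.0% if only 93/60 contribute at Month 3, with a ceiling of 84.0% if all 103/67 are observed.
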